##### 10.1.2. Population of Interest

The secondary pharmacokinetic analyses will be based on the Pharmacokinetic population, unless otherwise specified.

## 11. PHARMACODYNAMIC ANALYSES

### 11.1. Exploratory Pharmacodynamic Analyses

Endpoint / Variables

 
• Maximum observed change from baseline in EPO
 
• Maximum observed % change from baseline in VEGF
 
• Change from baseline in hematocrit, RBC count, and reticulocyte count
 

Planned Exploratory Displays

 
• Observed EPO and change from baseline in EPO will be summarized using mean, standard deviation, minimum, P25, median, P75, and maximum by visit, sample time, PD visit dose, and treatment group. Maximum observed post-baseline EPO and maximum observed change from baseline in EPO will be summarized using mean, standard deviation, minimum, P25, median, P75, and maximum by PD visit dose and treatment group.
 
• Observed VEGF will be summarized using geometric mean, CV(%), 95% CI, minimum, P25, median, P75, and maximum by visit, sample time, PD visit dose, and treatment group. Percent change from baseline in VEGF will be summarized using geometric mean, 95% CI, minimum, P25, median, P75, and maximum by visit, sample time, PD visit dose, and treatment group. Maximum observed post-baseline VEGF and maximum observed change from baseline in VEGF will be summarized using geometric mean, CV(%) (for maximum observed VEGF only), 95% CI, minimum, P25, median, P75, and maximum by PD visit dose and treatment group. (Summary statistics for VEGF will be calculated based on log-transformed values. See Section 5.2.2 for details of log-transformation.)
 
• Change from baseline in hematocrit, RBC count, and reticulocyte count are included in the summary of clinical laboratory analyses described in Section 8.4.
 

## 12. PHARMACOKINETIC / PHARMACODYNAMIC ANALYSES

- The primary goal of this analysis is to characterize the pharmacokinetic/ pharmacodynamic relationship of parent daprodustat and efficacy and safety endpoints in the “All Randomized (ITT)” or the “Pharmacokinetic” population from this study. Please refer to Section 7.4, Section 8.2, Section 10.1 and Section 11.1 for further details of related PK/PD analyses. Any changes to the proposed analyses would be described in the CSR.

## 14. APPENDICES

### 14.1. Appendix 1: Protocol Deviation Management and Definitions for Per Protocol Population

All deviations are to be tracked in GSK Protocol Deviation Management System (PDMS). Protocol deviations will be reviewed by the study team and important protocol deviations will be identified according to the Protocol Deviation Management Plan.

#### 14.1.1. Exclusions from Per Protocol Population

Exclusions from the PP population include events that, if they should occur, might:

- Directly impact the hemoglobin efficacy endpoint; or
- Lead to permanent discontinuation of study treatment or study withdrawal and hence indirectly impact the efficacy endpoint by causing data to be missing.

The following criteria define the events which, if they occur prior to the end of the EP, may lead to exclusion of a subject from the PP population. Exclusions from the PP Population will be subject to blinded review by the study team. Protocol deviations meeting the exclusion criteria and programmatically-identified exclusions, including those, which are not considered to be protocol deviations, will be reviewed by the study team. The study team will also review the listing of unique concomitant medication terms to identify the prohibited medications. These reviews will occur before database has been unblinded for analysis.

A subject meeting any of the following criteria may be excluded from the Per-Protocol population:

Number	Exclusion Description
01	Baseline HemoCue Hgb value outside of Randomization (Day 1) Hgb entry criteria range
02	Less than 5 out of 7 scheduled evaluable  Hgb values  from the EP
03	Non-compliance with study treatment (compliance category of under compliant or over compliant) during the EP, based on eCRF study treatment and compliance record forms
04	Inadequate iron status during EP, defined as ferritin $\leq$ 100 ng/mL on two consecutive scheduled visits or TSAT $\leq$ 20% on two consecutive scheduled visits
05	Subject received prohibited medication  for more than two weeks during EP

#### NOTES:

1. Based on central laboratory Hgb values. If central laboratory Hgb value is missing, a non-missing HemoCue Hgb value will be used.
2. See Section [14.6.3](#).
3. Prohibited medications include strong inhibitors of CYP2C8 (e.g., gemfibrozil) and strong inducers of CYP2C8 (e.g., rifampin/rifampicin).

## CONFIDENTIAL

204837

**14.2. Appendix 2: Schedule of Activities****14.2.1. Protocol Defined Schedule of Events****14.2.1.1. Schedule of Activities for Participants on Randomized Study Treatment**

Procedure Visit window of $\pm 3$ days for Weeks 2 to 8, and $\pm 1$ week for all other visits. All visit timings are relative to Day 1. All assessments will be performed pre-dialysis unless otherwise specified.	Screening (Week -4)	Treatment Period: Day 1 through Week 52					Follow-up Visit (4 to 6 weeks after last dose)
		Day 1 	Full Study Visit Week 4, 16, 28, 40	Abbreviated Study Visit Week 2, 6, 8, 12, 20, 24, 32, 36, 44, 48	Week 52	Unscheduled 	
Informed consent	X						
IRT system transaction 	X	X	X	X	X	X	X
Inclusion and exclusion criteria	X	X					
Randomization 		X					
Study Treatment Dispensing 		X	X	X 		X 	
Study Treatment Compliance 			X	X 	X	X 	
Participant reminder to report changes in health 		X					
Medical history (including past and current medical conditions, hospitalization and transfusion) 	X						
Demography, height	X						
Weight (pre- and post-dialysis) and EDW 	X	X	X	X	X	X	X
SBP/DBP, HR (pre- and post-dialysis)	X	X (triplicate)	X	X	X (triplicate)	X	X
Kt/Vurea 		X	X		X		
12-lead ECG 	X				X		
Ultrasound of kidneys and adrenal glands 	X						
Estradiol and FSH (females only, if required) 	X						
Serum pregnancy test (WOCBP only) 	X	X	X		X		X
HemoCue Hgb	X	X	X	X	X	X	
Hematology 	X	X	X	X (Hgb only)	X	X	X

## CONFIDENTIAL

204837

Procedure Visit window of $\pm 3$ days for Weeks 2 to 8, and $\pm 1$ week for all other visits. All visit timings are relative to Day 1. All assessments will be performed pre-dialysis unless otherwise specified.	Screening (Week -4)	Treatment Period: Day 1 through Week 52					Follow-up Visit (4 to 6 weeks after last dose)
		Day 1 	Full Study Visit Week 4, 16, 28, 40	Abbreviated Study Visit Week 2, 6, 8, 12, 20, 24, 32, 36, 44, 48	Week 52	Unscheduled 	
Clinical chemistry 	X	X	X		X	X	X
Ferritin, total iron and UIBC 	X	X	X		X		X
Lipids (non-fasting) 		X	X		X		
iPTH, hsCRP, HbA1c 		X	Wk 28		X		
Hepcidin 		X	Wk 4, 16, 28		X		
PD: EPO, VEGF 		X	X (once from Wk 28 to Wk 52) 				
PK		X	X (once from Wk 8 to Wk 52) 				
Stored samples for biomarkers 		X	Wk 28		X		
Genetic sample 		X					
Patient Global Impression of Severity (PGI-S) 		X	Wk 28	Wk 8, 12	X		
Patient Global Impression of Change (PGI-C) 			Wk 28	Wk 8, 12	X		
Non-serious AEs, SAEs, AEs of Special Interest, clinical events	X 	X	X	X	X	X	X
Concomitant medication review	X	X	X	X	X	X	X
Iron therapy, transfusions, rescue medications 	X	X	X	X	X	X	X
Hospitalization or kidney transplant 			X	X	X	X	X

DBP, diastolic blood pressure; ECG, electrocardiogram; EDW, estimated dry weight; FSH, follicle stimulating hormone; HbA1c, glycated hemoglobin; HR, heart rate; hsCRP, high sensitivity C-reactive protein; iPTH, intact parathyroid hormone; PD, pharmacodynamics; PK, pharmacokinetics; SBP, systolic blood pressure; UIBC, unsaturated iron binding capacity; VEGF, vascular endothelial growth factor; WOCBP, woman of childbearing potential.

Note: Pre-dialysis assessments should be performed in the following order, where applicable: patient reported outcomes, ECG, BP/HR, blood sample collection.

- All assessments to be performed pre-dose.
- If additional study treatment is required prior to the next scheduled study visit, it is not necessary to perform the unscheduled visit assessments other than dispensing study treatment.
- Study treatment will be dispensed every 4 $\pm$ 1 weeks, with the exception that it may be every 2 weeks  $\pm$  3 days up to the Week 6 visit. An IRT transaction will be required to dispense study treatment. Additional IRT transactions may occur if needed to dispense additional study treatment.
- In circumstances where randomization of an eligible participant cannot be completed at the Day 1 visit, the visit may be rescheduled up to 1 week later. Clinical laboratory assessments performed at the original visit, no more than 1 week prior, do not need to be repeated, except for the HemoCue hemoglobin and the Q2 hemoglobin.

**CONFIDENTIAL**

204837

5. Study treatment will be dispensed, i.e., allocated to a specific participant, and stored at the dialysis center or research site. Participant may take study treatment tablets at home in preparation for PD visit. See protocol Section 7 for further study treatment details.
6. In circumstances where a new supply of study treatment (including a new dose) cannot be dispensed on the day of the study visit, the new supply of study treatment can be dispensed at the next dialysis session. Prior study treatment should be continued unless on dose interruption, e.g., Hgb  $\geq 12$  g/dL. Compliance is deferred until study treatment is returned.
7. At the Week 2, Week 6 or unscheduled visits, if dose is not changed, new study treatment does not need to be dispensed and use of existing study treatment is continued. Compliance checking is required if new study treatment is dispensed.
8. Participant will be instructed to promptly notify site staff in the event of any changes to his or her health. Health changes include new symptoms, medical problems (e.g., pregnancy, hospitalization), and medication changes.
9. Medical history (including CV medical history/risk factors) will be assessed at screening (Week -4). Medical history will be re-assessed at Day 1 to confirm eligibility prior to randomization.
10. Estimated Dry Weight (EDW) to be recorded in the eCRF only at Day 1, full study visits, and Week 52.
11. A historical Kt/Vurea measurement within the last 12 weeks can be used. If a Kt/Vurea measurement is not available, then a urea reduction ratio (URR) measurement is acceptable.
12. The Week -4 (screening) ECG must be performed pre-dialysis, and may be performed on any dialysis day from the Week -4 visit to the Day 1 visit, except during the first dialysis session of the week. The result of the screening ECG, including physician interpretation, must be available to confirm eligibility prior to randomization. All other ECG assessments may be performed either pre- or post-dialysis. See protocol Section 9.4.3..
13. Ultrasound of the kidneys and adrenal glands will be performed between the Week -4 and Day 1 visits. If the results of the kidney and adrenal ultrasound require follow-up testing, then the screening period may be extended by 1 additional week. A documented ultrasound of the kidneys within the 6 months prior to screening may be used to assess entry criteria, provided the size and cyst category has been reported. If a more sensitive imaging study [e.g., magnetic resonance imaging (MRI), computed tomography (CT)] has been performed within this timeframe and a report is available, this may be used in place of the ultrasound. See protocol Section 9.4.4..
14. Only required to confirm menopausal status if in question.
15. Repeat pregnancy test prior to study treatment re-administration if study treatment was interrupted for >7 days and there was also a lapse in contraceptive use, regardless of the reason for the interruption.
16. In Argentina only, pregnancy testing will be performed every 4 weeks for WOCBP as required by local law.
17. See details for laboratory assessments in protocol Section 9.4.5.
18. HbA1c assessment is applicable only for participants with diabetes on Day 1 or diagnosed during the study.
19. At each visit specified in the table, a hepcidin sample will be collected prior to dosing with either study treatment and prior to administration of any iron supplementation.
20. Post-baseline PD samples (i.e., EPO and VEGF) may be taken during any week from Week 28 to Week 52, inclusive, preferably at the earliest opportunity. See protocol Section 9.6 for additional details and requirements for the collection of PD samples.
21. Post-baseline PK samples will be taken at any one of the post-baseline visits indicated in the table, preferably at the earliest opportunity. See protocol Section 9.5 for additional details and requirements for the collection of PK samples.
22. Biomarker samples will be collected and stored for potential future analysis for all participants, except if not permitted by local regulations or IRB/EC, or refused by participant.
23. Participation in genetics research is optional. A separate informed consent signature is required for participation. See protocol Section 9.7 for additional details.
24. Participants who are unable to or require assistance to read must not complete the questionnaires. See protocol Section 9.9 for additional details.
25. Only SAEs, which are assessed as related to study participation or a GlaxoSmithKline (GSK) product, are collected at this visit. See protocol Section 9.2.1 for additional details.
26. Record in the eCRF, if applicable.

## CONFIDENTIAL

204837

27. See details on Rescue in protocol Section 7.9.

#### 14.2.1.2. Schedules of Activities for Participants Who Permanently Discontinue Study Treatment

Procedure	Early Treatment Discontinuation Visit (within 2 weeks of discontinuing study treatment)	Day 1 through Week 52 	
		Week 4, 16, 28, 40, 52 ± 2 weeks	Un-scheduled
IRT system transaction	X	X	X
SBP/DBP, HR (pre- and post-dialysis)	X (triplicate)	X	X
12-lead ECG 	X		
Iron therapy, transfusions 	X	X	X
Serum pregnancy test (WOCBP only)	X 		
HemoCue Hgb	X	X	X
Hematology 	X	X	
Clinical chemistry 	X	X	
Ferritin, total iron, UIBC, lipids, iPTH 	X		
Hospitalization, kidney transplant 	X	X	X
Non-serious AEs, SAEs, AEs of Special Interest, clinical events	X	X	X
Review concomitant medications	X	X	X
PGI-S and PGI-C 	X		

- Participants will attend those study visits up to Week 52 which have not been completed at the time of early treatment discontinuation. Phone visits are acceptable in exceptional circumstances.
- ECG assessment may be recorded pre- or post-dialysis.
- Record in the eCRF, if applicable.
- Additional pregnancy test required at subsequent visit. Must be at least 4 weeks after the end of study treatment.
- See details for laboratory assessments in protocol Section 9.4.5.
- Participants who are unable to or require assistance to read must not complete the questionnaires. See protocol Section 9.9 for additional details.

### 14.3. Appendix 3: Assessment Windows

- Data for continuous variables that are not related to time-to-event will be summarized according to the scheduled visit time period for which they were recorded in the eCRF. Unscheduled assessments will not be slotted to a particular time point, but will remain as unscheduled if they are either summarized or listed unless otherwise specified (i.e. Hgb endpoints described in Section [14.6.3](#) and BP endpoints described in Section [14.6.4](#)).

## 14.4. Appendix 4: Study Phases and Treatment Emergent Adverse Events

### 14.4.1. Study Phases

Assessments and events will be classified according to the time of occurrence relative to the treatment start and stop dates and last non-zero dose date (see Section 14.6.1).

#### 14.4.1.1. Study Phases for Hgb, Iron Parameters, IV Iron Dose Endpoints, Iron Use Summaries, Transfusion and PRO Data

Study Phase	Definition
Pre-Treatment	Date $\leq$ Study Treatment Start Date
On-Treatment	Study Treatment Start Date < Date $\leq$ Study Treatment Stop Date + 1 day
Post-Treatment	Date > Study Treatment Stop Date + 1 day
Post-Randomization	Randomization Date < Date

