**NOTES:**

- If the treatment stop date is missing and the treatment start date is non-missing, and Date > Treatment Start Date, then the assessment will be considered to be On-Treatment

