#### 14.4.1.3. Study Phases for BP, Lipid Parameters, Clinical Chemistry, Hematology, Other Laboratory Tests, Hepatobiliary (Liver), ECG and Vital Signs Data

Study Phase	Definition
Pre-Treatment	Date $\leq$ Treatment Start Date
On-Treatment	Treatment Start Date < Date $\leq$ Last Non-Zero Dose Date + 1 day
Post-Treatment	Date > Last Non-Zero Dose Date + 1 day
Post-Randomization	Randomization Date < Date

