**NOTES:**

- If the last non-zero dose date is missing and the treatment start date is non-missing, and Date > Treatment Start Date, then the assessment will be considered to be On-Treatment
- Post-dialysis BP measured on treatment start date is considered on-treatment

CONFIDENTIAL

204837

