## 14.6. Appendix 6: Derived and Transformed Data

### 14.6.1. General

Multiple Measurements at One Time Point
 
 
• Mean of the measurements will be calculated and used in any derivation of summary statistics but if listed, all data will be presented. 
 
○ Triplicate BP and HR measurements are expected at certain time points (See Section 14.2.1)
 
 
 
• Subjects having both High and Low values for Normal Ranges at any post-baseline visits for safety parameters will be counted in both the High and Low categories of “Any visit post-baseline” row of related summary tables. This will also be applicable to relevant Potential Clinical Importance summary tables.
 

Randomization Date
 
 
• Date subject was randomized
 

Treatment Start Date
 
 
• First randomized treatment dose start date
 

Last Non-Zero Dose Date
 
 
• Date of last actual dose of active study treatment from the eCRF Study Treatment/Compliance Record Form. 
 
○ The dose steps used by the dosing algorithm described in the protocol include a dose hold or a zero dose. If subjects are assigned by the algorithm to a zero dose, they only receive placebo and saline, and do not receive active study treatment for that period. When a dose interruption is required, both active treatment and placebo/saline will be interrupted. Hence, it would be possible for a subject to complete the study, while still following the dosing algorithm, but not actually taking any active study treatment. The last non-zero dose date, then captures the latest date in the study that a subject physically took a dose of active study treatment.
 
 
 

Treatment Stop Date
 
 
• Calculated as the latest study treatment dose stop date, after excluding the records for missed dose.
 

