
End of Treatment Value
 
 
• Only defined for subjects with a non-missing treatment start date
 
• Hgb, iron, transfusion and PRO parameter: the latest value on or before the treatment stop date + 1 day.
 
• Blood pressure, central laboratory, and vital signs parameters: the latest value on or before the last non-zero dose date + 1 day.
 

CONFIDENTIAL

204837

Study Completion/Withdrawal Date

 
Date of withdrawal for subjects withdrawing (i.e., subjects who actively withdraw or are deemed lost to follow-up) from study or date of completion of study for subjects who complete the study. 
 
Note: Subjects who die while on study are considered as having completed the study
 
 
 

Planned/Actual Visit Dates

 
Planned/actual visit dates will be defined as follows: 
 
Week 28 date: Non-missing Week 28 visit start date (from SV domain), otherwise randomization date + 28*7
 
Week 36 date: Non-missing Week 36 visit end date (from SV domain), otherwise randomization date + 36*7
 
Week 52 date: Non-missing Week 52 visit end date (from SV domain), otherwise randomization date + 52*7
 
 
 

Stabilization Period
Defined as the period between and including the randomization date + 1 day - <Week 28 visit, using planned/actual dates.
Alternative Evaluation Period (Alt. EP)
Defined as the period between and including Week 28 visit – Week 36 visit, using planned/actual dates.
Evaluation Period (EP)
Defined as the period between and including Week 28 visit – Week 52 visit, using planned/actual dates.
Study Day

 
Calculated as the number of days from randomization date: 
 
Ref Date = Missing → Study Day = Missing
 
Ref Date < Randomization Date → Study Day = Ref Date – Randomization Date
 
Ref Date ≥ Randomization Date → Study Day = Ref Date – (Randomization Date) + 1
 
 
 

Treatment Day

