**14.6.3.5. Dose Adjustment Scheme Endpoints**

Dose Adjustment Scheme Endpoints
General

• The IRT system assigns all study treatment doses in accordance with the dose adjustment scheme specified in the protocol.

• During the study, it is possible for subjects to change study treatment doses at both scheduled and unscheduled visits.

• Sites are instructed to complete an exposure record for every dose taken/planned.

CONFIDENTIAL

204837

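### The one-day on-treatment window is shorter than the two-day gap between sessions on a three-session week, so a completer's Week 52 value is post-treatment unless a dose is given that day, and the documents conflict on that

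*SAP*

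**What the plan says.** SAP 14.4.1.1 covers hemoglobin (Hgb), iron parameters, IV iron, transfusions and patient-reported outcomes. Its on-treatment period closes at "Study Treatment Stop Date + 1 day". SAP 14.4.1.3 covers blood pressure (BP), laboratory, ECG and vital-sign data and closes at "Last Non-Zero Dose Date + 1 day". The one note in each section that extends the window begins "If the treatment stop date is missing and the treatment start date is non-missing" and "If the last non-zero dose date is missing and the treatment start date is non-missing" respectively. Each concerns a missing date, not a completer's last scheduled visit.

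SAP 14.6.1 defines the two anchor dates. The treatment stop date is "Calculated as the latest study treatment dose stop date, after excluding the records for missed dose"; the last non-zero dose date is the "Date of last actual dose of active study treatment". The same section takes the end-of-treatment value for BP, laboratory and vital-sign parameters as "the latest value on or before the last non-zero dose date + 1 day".

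On recording, SAP 14.6.3.5 says "Sites are instructed to complete an exposure record for every dose taken/planned". Protocol section 9 keeps study visits off the first dialysis session of the week; for a Monday-Wednesday-Friday participant the visit is on Wednesday or Friday.

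**The concern.** Tablets are taken on dialysis days, so on a three-session week the dose before a permitted visit is two days earlier. A one-day window cannot reach that visit. At visits before Week 52 this does no harm, because dosing continues and the stop date lies later. At Week 52 it matters: if the last dose was at the previous session, the final assessment of someone who completed treatment as planned is labelled post-treatment.

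At stake, if no dose is given on the Week 52 day:

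- **PGI-S and PGI-C at Week 52.** SAP section 9 uses on-treatment values only and plans no on/off-treatment version. The previous scheduled value is Week 28.
- **End-of-treatment BP.** The analysis is on-treatment only (SAP 8.1). The value falls back from the Week 52 triplicate to the single Week 48 reading, so no participant is lost but the value changes.
- **On-treatment laboratory and iron summaries at Week 52.** The previous scheduled chemistry, lipid, ferritin and iron values are at Week 40; hsCRP, iPTH and hepcidin are at Week 28.
- **Evaluable-Hgb analyses.** These cover time in range, responders and the per-protocol rule requiring 5 of 7 evaluable values.

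**Working it through.** **Planned doses (SAP 14.6.2.4).** Completed intervals carry 6 tablet doses from Day 1, 6 from each of Weeks 2, 4 and 6, and 12 from each of the 11 visits from Week 8 to Week 48.

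6 + 3 x 6 + 11 x 12 = 6 + 18 + 132 = 156 = 52 x 3.

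The count fills 52 weeks exactly, and no row adds a dose at Week 52.

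**Where the last 12 doses fall.** Take Monday-Wednesday-Friday sessions with Week 48 as day 0.

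- Wednesday visit: days 0, 2, 5, 7, 9, 12, 14, 16, 19, 21, 23, 26.
- Friday visit: days 0, 3, 5, 7, 10, 12, 14, 17, 19, 21, 24, 26.

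Both end on day 26. Week 52 is day 28, so the gap is 28 - 26 = 2 days. Tuesday-Thursday-Saturday gives the same result for both permitted sessions.

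**Classification under 14.4.1.1, dose-by-dose records.**

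- No dose on the Week 52 day: stop date + 1 = day 27, before day 28, so post-treatment.
- Dose on the Week 52 day: gap 0, so on-treatment.

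**Classification under 14.4.1.3, counted from the last active dose.**

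- Daprodustat: gap 0 with a Week 52 dose, 2 days without.
- Once-weekly epoetin, dosing continuing on the Week 52 day: for injections on Monday, Wednesday or Friday the gap is 2, 0 or 5 days at a Wednesday visit, and 4, 2 or 0 at a Friday visit.
- Once-weekly epoetin, no Week 52 dose: 2, 7 or 5 days, and 4, 2 or 7 days.

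These are possible gaps, not frequencies.

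**Per-protocol rule.** Scheduled evaluation-period values are at Weeks 28, 32, 36, 40, 44, 48 and 52, which is 7. Without Week 52 at most 6 can be evaluable, so the number of further missing values tolerated before exclusion falls from 7 - 5 = 2 to 6 - 5 = 1.

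**Time in range (SAP 14.6.3.1).** With Week 28 as day 0, Week 48 is day 140 and the last dose is day 166. The denominator is 166 + 1 - 0 = 167 days. Without Week 52, 167 - 140 = 27 days (27/167 = 16%) follow the last scheduled evaluable value.

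**The case against.** The strongest reply is that Week 52 is a dosing day. Several passages assume this or something close to it:

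- SAP 7.4.1 lists an assigned dose at Week 52, and SAP 14.6.3.5 defines an assigned dose by an exposure record starting on or after the visit.
- Protocol 9.5.1 and 9.6.1 allow PK and PD sampling visits, with dosing, up to and including Week 52.
- SAP 14.6.3.1 admits evaluable, hence on-treatment, Hgb values up to four weeks after Week 52.
- SAP 14.6.3.3 provides for completing the study on the treatment stop date.
- A footnote to Protocol Table 7 runs the dose-adjustment visits through Week 52.

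The blank in the Week 52 dispensing cell is also weak evidence, because drug is held at the site and visits may be up to five weeks apart. All of this stands, and it rules out asserting that Week 52 values are lost. It does not remove the conflict with the 156-dose count, and no rule protects the value if no dose is given.

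A reader might instead infer that exposure records span the interval and stop on day 27, which would rescue the value under 14.4.1.1. The exposure listing has start dates, stop dates and durations (SAP 6.2.6), and SAP 14.6.2.4 refers to gaps between records. But 14.6.2.4 and 14.6.3.5 also describe individual dose records. The 3/7 multiplier in 14.6.2.4 applies to uncompleted visits and computes expected doses; it defines no stop date and is not evidence for day 27. A span would not help 14.4.1.3 in any case, because that section counts from the last actual active dose.

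Two further objections hold. A Week 52 rule without a limit would reclassify participants on a temporary interruption (Protocol 7.2.4). And the per-protocol effect may never arise, because SAP section 4 drops that analysis if the set exceeds 80% of those randomized.

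**Conclusion.** The point holds as a conflict to be reconciled, with a cheap improvement to the window. On the dose count, dose-by-dose records and the dispensing schedule, the stated rule makes an on-schedule completer's Week 52 value post-treatment by one day. On the passages that imply a Week 52 dose, it does not. How many participants are affected cannot be computed from the documents. The arithmetic assumes three sessions a week; participants dialysed more often may have a one-day gap.

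The consequences are confined to secondary, supportive and descriptive analyses outside the multiplicity hierarchy. A reader might infer damage to the primary result, but the primary analysis uses Hgb both on and off treatment (SAP 7.1.5.1). The Week 52 Hgb and BP repeated-measures models also have on/off-treatment versions that are unaffected.

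A reader might also infer bias between arms. With no Week 52 dose, both arms lose the value on a three-session week. The arms differ under 14.4.1.3 only if dosing continues on the Week 52 day and a once-weekly epoetin injection falls on another weekday. Protocol 7.1 and 7.2 make that less likely, because Day 1 is timed to the next scheduled rhEPO dose and dose changes start on the visit day.

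**What to change.** Before unblinding:

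1. In SAP 14.4.1.1, 14.4.1.3 and the End of Treatment Value entry of 14.6.1, class the scheduled Week 52 assessment of Hgb, patient-reported, BP, laboratory, iron-parameter, ECG and vital-sign data as on-treatment for participants who did not permanently discontinue early. Require it to fall within 7 days (one weekly dosing interval) of the treatment stop date (14.4.1.1) or the last non-zero dose (14.4.1.3), so that longer interruptions, holds and zero-dose periods are not reclassified.
2. Leave the one-day rule as it is for IV iron, iron use, transfusions, the adverse-event window and the time-in-range denominator. Cap time-in-range numerator days at that denominator's end date; otherwise interpolating to Week 52 could give 168/167 = 100.6%.
3. State whether the Week 52 day carries a dose record, and reconcile the passages that differ.

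The cost is SAP wording and derivation code, with no new data. The rule changes nothing where a dose of active treatment is given on the Week 52 day, and the principal secondary IV iron endpoint keeps its single definition. The downside is that a value taken up to 7 days after the last active dose counts as on-treatment.
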